5.5 Study Drug Exposure and Compliance

5.5.1 Exposure

Duration of exposure to study drug is defined for each subject as the last study drug dose date minus the first study drug dose date plus 1 day. The number and percentage of subjects in the safety population with study drug duration of ≥ 52 days will be summarized.

5.5.2 Compliance

At each visit (starting with the Week 4 visit) during the Treatment Period, the total number of tablets dispensed and returned is recorded. The compliance, defined as adherence for study drug (GLE/PIB) during the treatment period, will be calculated as the percentage of tablets taken relative to the total tablets expected to be taken. The total number of tablets expected to be taken will be equal to the total number of tablets that should have been taken per the protocol for the duration that the subject was in the Treatment Period (date of last dose of study drug – date of first dose of study drug + 1). Study drug interruptions recorded on the eCRF will not be subtracted from the duration. A subject is considered to be compliant (adherent to treatment) if the percentage is between 80% and 120%.

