2.2 Benefits and Risks to Subjects

Chronic HCV infection is a major global health problem impacting quality of life, morbidity, as well as mortality. Evidence suggests that effective treatment of HCV can cure the infection as well as improve liver function.¹⁻³

The GLE/PIB regimen is an oral, RBV-free pangenotypic regimen that provides high SVR₁₂ rates $\geq 95\%$ in subjects with compensated liver disease infected with HCV GT1 – GT6, with the majority of subjects treated for 8 – 12 weeks. Low relapse rates $< 3\%$ were observed in GT1 – GT6 treatment-naïve subjects without cirrhosis following 8 weeks of treatment, demonstrating no benefit of an additional 4 weeks of treatment. Among these subjects, an 8-week regimen of GLE/PIB achieved SVR rates similar to 12 weeks of treatment and to the only currently approved pangenotypic HCV regimen. However, GLE/PIB achieved similar efficacy with a significant reduction of the duration of treatment, which may improve subjects' adherence, access to treatment, and convenience, and also reduce the burden associated with additional medical visits and procedures.

Based on safety data from the registrational and supportive clinical trials where 2369 HCV-infected subjects were treated, the fixed-dose combination of GLE/PIB demonstrated a favorable safety profile. The most frequent GLE/PIB related adverse events (AEs) include headache, fatigue and nausea, and were mostly Grade 1 (mild) in severity. Grade 3 or higher AEs and serious adverse events (SAEs) were uncommon, occurring in 3.8% and 3.1%, of subjects, respectively. Similarly, the overall rate of study drug discontinuations due to AEs was low (0.5%).^{8,9} Safety in subjects with cirrhosis was shown to be similar to subjects without cirrhosis.^{8,9}

Potential risks that may occur with GLE/PIB therapy include hepatotoxicity, development of viral resistance, and the development of toxicities from drug-drug interactions (DDIs). The potential risks for GLE/PIB can be monitored, mitigated and managed in clinical practice.

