3.4 Exploratory Endpoints

- SVR₁₂ in subjects with APRI ≤ 0.7 and APRI ≤ 0.5 based on ITT population
- Percentage of subjects with virologic failure with Fibrotest > 0.75 based on ITT population
- Percentage of subjects with SVR₁₂ by key groups (HCV genotype and subtype; age) based on ITT population
- Adherence to treatment based on ITT population

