5.7 Study Drug

Identity of Study Drug

Information about the study drug to be used in this study is presented in [Table 1](#).

Table 1. Identity of Study Drug

Study Drug	Manufacturer	Mode of Administration	Dosage Form	Strength
Glecaprevir/pibrentasvir	AbbVie	Oral	Film-coated tablet	100 mg/40 mg

Three tablets of GLE/PIB combination will be taken QD, beginning on Day 1 (baseline), and should be taken at approximately the same time each day. The study drug must be taken with food.

Glecaprevir/pibrentasvir combination tablets will be packaged in bottles with quantities sufficient to accommodate the study design. Each kit label will contain a unique kit number. This kit number which is assigned to a subject identifies the appropriate study drug to be dispensed at the subject's corresponding study visit. Each kit will be labelled as required per country requirements. Labels must remain affixed to the kits. All blank spaces on the label will be completed by the site staff prior to dispensing to the subjects.

Subject will be instructed to return all drug containers (even if empty) to the study site personnel at each study visit. The study site personnel will document compliance.

AbbVie will not supply drug other than GLE/PIB combination.

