In the registration studies different SVR₁₂ rates based on mITT population have been observed among naïve non cirrhotic GT3-infected subjects and non-GT3-infected subjects for 8 weeks of GLE/PIB treatment. In these studies, approximately 98.9% and 96.2% SVR₁₂ has been observed among non-cirrhotic, treatment naïve chronic HCV GT1, GT2, GT4, GT5, and GT6-infected subjects and GT3 subjects assigned to 8 weeks of treatment, respectively.¹⁻³ Hence, for the non-cirrhotic GT1 – GT6-infected subjects, based on mITT population, the historical SVR₁₂ rate of 98.4% is estimated based on a weighted average of 80% GT1, GT2, GT4, GT5, and GT6 historical rate and 20% GT3 historical rate. To establish cut off for efficacy based on mITT population, a margin of 6% is applied to the historical control rate of 98.4%, resulting in a threshold of 92.4%.

Historical SVR₁₂ rate based on ITT population depends on the non-virologic failure in a study. Study-to-study variability has been observed in non-virologic failure rates, and is typically around 1%. The observed rate of non-virologic failure in the registrational program is 1.2% (29/2369).¹⁻³ For this reason, this study assumes that the historical SVR₁₂ rate based on ITT population for treatment naïve non-cirrhotic subjects is 97.4% (with 1% non virologic failure). To establish cut off for efficacy based on ITT population, a margin of 6% is applied to the historical control rate of 97.4%, resulting in a threshold of 91.4%.

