6.4 Other Efficacy Analyses

The following additional efficacy endpoints will be summarized and analyzed for the ITT population:

- The percentage of subjects with HCV RNA < LLOQ at each post-baseline visit in the Treatment Period (using data as observed);
- The percentage of subjects with SVR₄;
- Adherence to treatment;
- The percentage of subjects in the ITT population with virologic failure by baseline FibroTest score (≤ 0.75 or > 0.75);
- The percentage of subjects in the ITT population with on-treatment virologic failure by HCV genotype;

- The percentage of subjects in the ITT population with post-treatment relapse by HCV genotype.

In the above analyses, the percentage of subjects with a two-sided 95% Wilson score interval will be summarized. Imputations for missing data will be performed as described in Section 4.7 for SVR, where a missing response will be imputed as a failure after performing the described imputation. All other endpoints will be presented using data as observed.

A summary of the subjects who completed treatment and relapsed will be prepared displaying the number of subjects relapsing overall and by SVR visit window (within the SVR₄ window or within the SVR₁₂ window), including the subject number and the SVR visit window corresponding to the first occurrence of relapse. A similar listing will be prepared for subjects who prematurely discontinued treatment and relapsed after having HCV RNA < LLOQ at their Final Treatment Visit.

Descriptive statistics (mean, standard deviation, median, minimum, and maximum; number and percentage) will be presented for exposure during the treatment period. Compliance (adherence) will be calculated for each subject and summarized with the mean, median, standard deviation, minimum, and maximum for each treatment arm and overall. A listing of compliance for each subject will be provided. The percentage of compliant subjects will be summarized based on data as observed. An additional summary of the percentage of compliant subjects will be provided where subjects who are missing study drug accountability records will be imputed as non-compliant.

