6.5 Efficacy Subgroup Analyses

The number and percentage of subjects with SVR₁₂ in the ITT and mITT populations will be presented for the following key subgroups:

- Baseline APRI (≤ 0.7 or > 0.7) and (≤ 0.5 or > 0.5);
- HCV genotype (1, 2, 3, 4, 5, or 6) and available subtype;
- Age (< 65 or ≥ 65 years) and (< 75 or ≥ 75 years);
- Baseline FibroTest score (≤ 0.75 or > 0.75);
- Adherence to treatment (yes/no).

The two-sided 95% Wilson score confidence interval will be produced if there are at least 10 subjects in the subgroup.

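### Does the adherence ratio in SAP 5.5.2 mislead because expected tablets are counted only up to the last dose taken?

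*SAP*

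**What the plan says.** Protocol 3.4 and SAP 4.3.3 list an exploratory endpoint, "Adherence to treatment based on ITT population", without defining it. SAP 5.5.2 supplies the definition. It equates compliance with adherence to study drug in the treatment period and takes the ratio of tablets taken to tablets expected. Tablets are expected "for the duration that the subject was in the Treatment Period (date of last dose of study drug" minus date of first dose, plus 1). It then adds: "Study drug interruptions recorded on the eCRF will not be subtracted from the duration". A ratio from 80% to 120% counts as adherent.

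The result is used in two places. SAP 6.4 summarises compliance and the percentage of compliant subjects, with an additional version in which "subjects who are missing study drug accountability records will be imputed as non-compliant". SAP 6.5 lists "Adherence to treatment (yes/no" among the SVR12 subgroups for the ITT and mITT populations, and gives a Wilson interval only where a subgroup has at least 10 subjects.

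Early stopping is reported elsewhere:

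- SAP 5.4 tabulates premature discontinuation of study drug, by reason.
- SAP 5.5.1 gives the number and percentage with a duration of at least 52 days.
- SAP 6.1 has a separate category of SVR12 non-response for subjects who stopped before 52 days without on-treatment virologic failure.
- SAP 6.4 summarises exposure and lists compliance by subject.

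**The concern.** The denominator ends with the last dose actually taken. Doses missed before that day count against the subject, but doses never taken after a permanent stop do not. Two subjects with the same total intake can therefore be classified in opposite ways, and someone who leaves an 8-week course after two weeks can be scored as fully adherent.

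If a reader took the endpoint to mean adherence to the whole course, the reported rate would be too high. In the ITT subgroup table, early stoppers with good intake would sit in the adherent stratum. The SVR12 contrast would narrow if they failed and widen if they reached SVR12. The ratio in SAP 5.5.2 is the only adherence measure defined, and none of the reports of early stopping feeds into it.

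**Working it through.** The documents state no adherence result, so there is no figure to reproduce.

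**Inputs.** Protocol 5.7: "Three tablets of GLE/PIB combination will be taken QD, beginning on Day 1 (baseline"), so 3 tablets a day. Protocol 4.1 and Appendix D: 8 weeks, with end of treatment on Day 56. SAP 5.5.2: limits of 80% and 120%. Usable tablet counts and complete returns are assumed.

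**Formulas.** For a subject with last dose on Day d:

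- SAP ratio = tablets taken / (3 × d).
- Course-based alternative = tablets taken / (3 × 56) = tablets taken / 168. The 80% limit is 0.8 × 168 = 134.4 tablets.

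**Full intake up to the last dose.**

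| Last dose | Tablets | SAP ratio | Share of 168 |
|---|---|---|---|
| Day 14 | 42 | 100% | 25.0% |
| Day 28 | 84 | 100% | 50.0% |
| Day 44 | 132 | 100% | 78.6% |
| Day 45 | 135 | 100% | 80.4% |
| Day 56 | 168 | 100% | 100% |

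**Equal intake, opposite class.** Days 1 to 44 and then a permanent stop: 132/132 = 100%, adherent. Days 1 to 43, a 12-day gap, then the Day 56 dose: 132/168 = 78.6%, not adherent. The arithmetic is right. But the first subject missed nothing while on drug and the second missed 12 days. A measure of dose-taking on treatment should separate them.

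**Day 44 is not a general boundary.** It applies to perfect intake only. A subject who stops on Day 50 with 128 tablets scores 128/150 = 85.3% under the SAP and 128/168 = 76.2% of the course, so that subject also changes class. Nor is every early stopper scored adherent: if all 168 tablets were dispensed and none returned, a Day 44 stopper scores 168/132 = 127%, above the upper limit.

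**How many subjects.** The documents do not give the share who stop early with good intake. Two rates from the earlier programme can be tried as assumptions:

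- Protocol 2.2: "the overall rate of study drug discontinuations due to AEs was low (0.5"%). 0.005 × 230 = 1.2 subjects.
- SAP 4.4: "The observed rate of non-virologic failure in the registrational program is 1.2% (29/2369"). 0.0122 × 230 = 2.8 subjects.

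This gives about 1 to 3 of 230, or 0.5 to 1.2 percentage points. Neither rate measures the quantity needed. The first is stopping for adverse events at any time, in a programme that included 12-week treatment and subjects with cirrhosis. The second, by the categories in SAP 6.1, can also include missing SVR12 data and reinfection in subjects who completed treatment.

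**Subgroup table, on invented counts.** Assume 9 ITT failures among 230 (the planning rates give 184 × 0.03 + 46 × 0.07 = 8.7), 5 other non-adherent subjects of whom 1 fails, and 2 early stoppers.

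| Rule | Adherent | Not adherent |
|---|---|---|
| SAP | 217/225 = 96.4% | 4/5 = 80.0% |
| 168 tablets, both stoppers fail | 217/223 = 97.3% | 4/7 = 57.1% |
| 168 tablets, both reach SVR12 | 215/223 = 96.4% | 6/7 = 85.7% |

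The adherent stratum moves by less than 1 point. The other stratum swings, but with 5 or 7 subjects it falls below the 10 that SAP 6.5 requires for an interval, so only a count and a percentage would appear.

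**The case for a change.** The strongest case for the concern starts from Protocol 2.2, which suggests that the shorter course may improve adherence. A ratio that ignores everything after the last dose cannot show whether subjects stayed on that course. The SAP calls the ratio adherence to treatment without saying that it applies only while on drug, and no table crosses it with duration of exposure. A second ratio against 168 tablets would need one derived variable from data already collected, and subjects stopped under protocol rules could be flagged.

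Part of this stands: the ratio does not measure persistence, and a reader who takes the label alone could misread it. But the remark in Protocol 2.2 compares a shorter with a longer regimen and does not define the endpoint. Reading the endpoint as completion of 168 tablets adds something that neither document says.

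The alternative also has a cost. Protocol 5.5 takes subjects with confirmed virologic failure off study drug. A fully compliant subject stopped for that reason on Day 28 would score 84/168 = 50.0% and be labelled non-adherent because treatment had failed. In an SVR12-by-adherence table that reverses cause and effect. A flag for virologic failure and the toxicity rules of Protocol 6.2 would not clearly cover the other stops in Protocol 5.5, such as investigator judgement or pregnancy.

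**Conclusion.** The concern does not hold. It reads the formula correctly, but the formula is explicit, internally consistent and a recognised kind of measure. Dose-taking while on drug and persistence to Week 8 are separate quantities, and the SAP reports both. Following the plan as written gives sound results.

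The size in this trial cannot be established from the documents. The figure of 1 to 3 subjects rests on proxy rates that do not measure early stopping with good intake, and the subgroup swing rests on assumed counts. In mITT the effect is smaller still: a subject who stops by Day 44 and misses SVR12 leaves that population unless on-treatment virologic failure was met (SAP 5.1 and 6.1). Both uses of the ratio are descriptive and lie outside the fixed testing sequence of SAP 4.6, so the 92.4% and 91.4% threshold tests are untouched. Whether to add a course-based summary is a choice on which statisticians can reasonably differ, and its absence is not a defect.

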6.0 Efficacy Analyses

6.1 General Considerations

Plasma HCV RNA levels will be determined for each sample collected by the central laboratory using the Roche COBAS[®] AmpliPrep/COBAS[®] TaqMan[®] HCV Quantitative Test, v2.0. The lower limit of detection (LLOD) and lower limit of quantification (LLOQ) for this assay (regardless of genotype) are both 15 IU/mL.

HCV RNA results that are detectable but not quantifiable are reported as "< 15 IU/ML HCV RNA DETECTED" and those that are undetectable are reported as "HCV RNA NOT DETECTED" in the database.

The notation "HCV RNA < LLOQ" is used to represent all HCV RNA values < 15 IU/mL, including values reported as "HCV RNA NOT DETECTED" or "< 15 IU/ML HCV RNA DETECTED." HCV RNA \geq LLOQ are all quantifiable values of 15 IU/mL or greater.

Definitions for Efficacy Endpoints

A confirmed quantifiable value during treatment is defined as any two consecutive HCV RNA measurements \geq LLOQ (or 100 IU/mL for **Breakthrough**), either both during treatment or at the final treatment measurement and the next consecutive post-treatment measurement. A confirmed quantifiable post-treatment value is defined as any two consecutive post-treatment HCV RNA measurements \geq LLOQ.

Breakthrough = confirmed HCV RNA \geq 100 IU/mL after HCV RNA < LLOQ during the Treatment Period; or confirmed increase from nadir in HCV RNA (two consecutive HCV RNA measurements > 1 log₁₀ IU/mL above nadir) at any time point during the Treatment Period. A single breakthrough value (\geq 100 IU/mL or > 1 log₁₀ above nadir) followed by lost to follow-up also will be considered a breakthrough (i.e., will not require confirmation).

EOT failure = HCV RNA \geq LLOQ at end of treatment with at least 6 weeks of treatment, where the HCV RNA value must be collected on or after Study Drug Day 36 and study drug duration \geq 36 days.

On-treatment virologic failure = **Breakthrough** or **EOT failure**.

SVR₄ = HCV RNA < LLOQ in the SVR₄ window (4 weeks after the last actual dose of study drug) without any confirmed quantifiable (\geq LLOQ) post-treatment value before or during that SVR window.

SVR₁₂ = HCV RNA < LLOQ in the SVR₁₂ window (12 weeks after the last actual dose of study drug) without any confirmed quantifiable (\geq LLOQ) post-treatment value before or during that SVR window.

Post-treatment relapse (i.e., **Relapse₁₂**) = confirmed HCV RNA \geq LLOQ between end of treatment and 12 weeks after last actual dose of study drug (up to and including the SVR₁₂ assessment time point) for a subject with HCV RNA $<$ LLOQ at Final Treatment Visit who completed treatment (defined as study drug duration \geq 52 days), excluding reinfection.

Virologic failure = On-treatment virologic failure or Post-treatment relapse (Relapse₁₂)

Only subjects who have at least one post-treatment HCV RNA value will be included in the analysis of relapse. For the analysis of relapse, completion of treatment is defined as any subject with study drug duration of 52 days or greater. If the last available post-treatment value is \geq LLOQ, then the subject will be considered a relapse (i.e., will not require confirmation).

HCV reinfection is defined as confirmed HCV RNA \geq LLOQ after the end of treatment in a subject who had HCV RNA $<$ LLOQ at Final Treatment Visit, along with the post-treatment detection of a different HCV genotype, subtype, or clade compared with baseline, as determined by phylogenetic analysis of the NS3 or NS5A, and/or NS5B gene sequences. Reinfection in the case of the same HCV subtype is defined as a clade switch, as indicated by the lack of clustering between the baseline and post-treatment sequences by phylogenetic analysis. If phylogenetic analysis is not possible due to technical difficulties, HCV reinfection may be determined with a confirmed HCV genotype or subgenotype switch by the Versant HCV Genotype Inno-LiPA Assay v2.0 or Sanger assay.

Reasons for SVR₁₂ Non-Response

Subjects who do not achieve SVR₁₂ (SVR₁₂ non-responders) will be categorized as having:

1. On-treatment virologic failure (see **On-treatment virologic failure** definition);

2. Relapse (defined according to the **Relapse₁₂** definition for subjects who complete treatment);
3. Prematurely discontinued study drug with no on-treatment virologic failure (defined as any SVR₁₂ non-responder who prematurely discontinued study drug [study drug duration < 52 days] and did not meet the **On-treatment virologic failure** or **Relapse₁₂** definition);
4. HCV reinfection (see definition described earlier);
5. Missing follow-up data in the SVR₁₂ window (defined as any subject who completed study drug without data in the SVR₁₂ window after applying the imputation rules and not meeting the definitions of [1], [2], [3], or [4]);
6. Other (defined as any SVR₁₂ non-responder not meeting the definitions of [1] – [5]).

6.2 Primary Efficacy Analysis

The primary efficacy endpoint is SVR₁₂ (HCV RNA < LLOQ 12 weeks after the last actual dose of study drug). The number and percentage of subjects in the mITT population achieving SVR₁₂ will be summarized and a two-sided 95% confidence interval will be calculated using the normal approximation to the binomial distribution. If the number of SVR₁₂ non-responders is less than five, then the Wilson's score method will be used to calculate the confidence interval. As a sensitivity analysis, Wilson's score method will be used to calculate the confidence interval if the number of SVR₁₂ non-responders is greater than or equal to five.

The efficacy of 8-week treatment duration for HCV GT1 – GT6 subjects with APRI ≤ 1 based on mITT population will be established if the lower boundary of two-sided 95% confidence interval for the percentage of subjects achieving SVR₁₂ is greater than 92.4%.

A summary of reasons for SVR₁₂ non-response (e.g., on-treatment virologic failure, relapse) in the mITT population will be provided. A listing of subjects who do not

achieve SVR₁₂ by reason for non-response will also be provided. A listing of subjects excluded from the mITT population will be provided.

6.3 Secondary Efficacy Analyses

The number and percentage of subjects in the ITT population achieving SVR₁₂ will be summarized and a two-sided 95% confidence interval will be calculated using the normal approximation to the binomial distribution. If the number of SVR₁₂ non-responders is less than five, then the Wilson's score method will be used to calculate the confidence interval. As a sensitivity analysis, Wilson's score method will be used to calculate the confidence interval if the number of SVR₁₂ non-responders is greater than or equal to five.

The efficacy of 8-week treatment duration for HCV GT1 – GT6 subjects with APRI ≤ 1 based on ITT population will be established if the lower boundary of two-sided 95% confidence interval for the percentage of subjects achieving SVR₁₂ is greater than 91.4%.

The number and percentage of subjects, along with two-sided 95% Wilson score intervals, with on-treatment virologic failure (defined as **On-treatment virologic failure**) and with post-treatment relapse (defined as **Relapse₁₂**) will be summarized overall for the ITT population.

